7.2.3 Follow-up

Two index date definitions will be applied as appropriate for each objective.

- Diagnosis index date is defined as a positive PCR test for SARS-CoV-2 (labCOVID-19) or a confirmed COVID-19 diagnosis(diagCOVID-19) whichever is the earliest.
- Treatment index date is defined as start of first systemic glucocorticoid treatment episode specifically for the treatment of COVID-19, irrespective of whether the patient is a prevalent or naïve user.

Follow up for all patients will begin from the index date until they experience the outcome of interest (endpoint, depending on the objective) or until cohort exit (date of censoring). The patients will be followed up for maximum 90 days or until censoring occurs, censoring criteria are:

- death
- patient exit (deregister) from a contributing data provider (GP practice)
- end of the database's data collection
- end of study period (latest data cut-off)

The lookback window for evaluating risk factors, medical history is 365 days and will be applied only to outpatient cohorts.

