7.3.2.3 Operationalization of exposure metrics

Cumulative duration

For glucocorticoids used in COVID-19 indication

Exposure to a treatment will commence on the date of the first qualifying record, subject to satisfying all inclusion criteria listed in section 7.2.2. Each drug exposure record has a start date and inferred end date, which is either explicitly entered or derived from other available information, such as days' supply or refills. Duration of each episode will be calculated as end date minus start date or directly from days' supply variable, whatever available. For each patient, the cumulative duration of use will be calculated as the sum of the duration of treatment episodes.

Table 3 Calculation of duration of use and end of treatment across databases

	IPCI	UK IMRD	Germany DA	Belgium LPD	SIDIAP	France LPD
If days_supply is missing	Use amount and dose extracted from the sig	Use daily dosage along with prescribed quantity	Impute with the most frequent daily dosage or DDD at a therapy level	Use calculated quantity/units_per_day.	Use the quantity, daily dosage and DDD of each drug	Use the quantity and daily dosage of each drug
If still missing	Use the DDD and prescribed quantity	Impute most frequent daily dose at the drug level	-	-	-	-
If still missing	Use the modal duration in the database					

DDD= defined daily dose; sig - the directions ('signetur') on the drug prescription as recorded in the original prescription (and printed on the container) or dispensing record from the physician.

Daily dose

For glucocorticoids used in COVID-19 indication, the prescribed daily dose at initiation of glucocorticoid (treatment index date) will be recorded and categorized in low and high dose. The definition of low dose and high dose will use the cut off defined by WHO in their prospective meta-

analysis from REACT subgroup (16), namely: 15 mg/d of dexamethasone, 400 mg/d of hydrocortisone, and 1 mg/kg/d of methylprednisolone.

The current recommendation is to use 10 mg of dexamethasone for maximum 10 days, administered orally or intravenously. In case glucocorticoids other than dexamethasone are administered, their dose will be converted in prednisolone equivalents as described:

<https://emedicine.medscape.com/article/2172042-overview>

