Only the first episode of exposure will be considered, patients being censored when they switch to another treatment (including switch to another glucocorticoid) or when follow up ends. Duration of follow-up for each treatment cohort will be summarized and will constitute the denominator for calculation of effect estimates. A persistence window of 7 days between drug utilization records for each study drug will be allowed considered as continuous exposure for the outcome's assessment.

In case that more than 70% of the patients are censored, a sensitivity approach will be applied for objectives 2 and 3 (see Section 7.7.8).

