7.7.8 Sensitivity analysis

For objective 2 and 3, with regards to the reference group for incidence rates

As a sensitivity analysis, the reference group for incidence rates will be replaced with ‘other immunotherapies’ (see Appendix 3 for details).

For prevalent users’ cohorts, the definition of remote users:

A sensitivity analysis to exclude those patients for whom short term duration of corticosteroid use (14 days) is identified prior to COVID-19 diagnosis.

For objectives 2 and 3, if the number of patients censored due to switching is higher than 70%, a sensitivity analysis will be performed, namely an intention to treat approach (ITT), such that after initial exposure is defined to allocate patients to one of the four treatment groups, the denominator is then person-time observed (irrespective of treatment status), rather than person-time treated.

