7.9 Limitations of the Research Methods

7.9.1 Study design limitation

COVID-19 diagnosis misclassification – the diagnosis of COVID-19 in absence of confirmatory test has a high likelihood to be misclassified as the disease symptoms are unspecific. This misclassification is more likely for patients treated in primary care, e.g., those with milder symptoms. In addition, with regards to the availability of results of PCR test for SARS-CoV-2, this is currently available in only one database (SIDIAP).

- **Mitigation:** Different definitions will be explored and compared as part of objective 4. We will base the main definition on definite diagnosis not on symptoms only and supplement with confirmatory tests when available

Confounding by indication and severity may occur when the different treatments are prescribed depending upon the physician's assessment of the patient's health status in relation to the outcome of interest. The risk of this confounding is high due to glucocorticoids being indicated in severe COVID-19 cases only and therefore correlated with the increase in severity.

- **Mitigation:** No comparative analysis will be performed. This confounding needs to be considered when interpreting the incidence rates obtained.

Selection bias occurs when there is a selective recruitment into the study of subjects that are not representative of the population intended to be studied, so that the association between exposure and outcome of interest is different in the included and excluded population.

- **Mitigation:** Minimal exclusion criteria will be used. In addition, we have included data sources with large or whole national coverage and both ambulatory and hospital setting.

Exposure to glucocorticoids in hospital setting might be underrepresented as glucocorticoid might be captured only as ward stock and not as individual dispensation.

On-treatment exposure classification was considered suitable for this study in order to facilitate comparison with clinical trials results. However, this way of classifying exposure does not consider subsequent treatments and might miss a deterioration of disease.

The **short duration of follow-up** will allow only the capture of acute adverse events.

Prescribing patterns of corticosteroids over time

Due to the short study period (1 year) any time series analysis cannot be undertaken, and the observed trends cannot be confirmed.

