If exposure to glucocorticoids as second or third treatment occurs very often, a large proportion of patients will be censored, leading to limited data to assess the outcomes of interest.

Mitigation – an ITT sensitivity analysis is proposed in case censoring is very large (>70%)

7.9.2 **Databases related limitations**

Linkage between primary and secondary care

Seven out of eight databases will not have linkage between primary and secondary setting, and a consequence of this is that patient follow up time will be fragmented. Especially in the hospital setting, the access to medical history of the patient is limited and the patients who had prior exposure of glucocorticoids in primary care risk to be misclassified as naïve users.

Primary care databases

Severe outcomes that lead to hospitalization are less likely to be captured., although hospitalization is captured in some of the primary care databases.

If patients are free to change general practitioners and they are not tracked across different GPs or if they are treated. In private practice, their exposure will be underestimated and the follow up will be fragmented.

As the hospital and ambulatory settings are not linked, patients who had prior exposure of glucocorticoids in hospitals will be misclassified as naïve users.

Hospital setting databases

As the lookback period in the hospital setting is in general absent or reduced, there will be an under-ascertainment of baseline comorbidities.

Mortality data

The mortality information (vital status) is under-captured in some data sources. Three of them, DA Germany, LPD France and LPD Italy do not record vital status at all. For SIDIAP, the vital status comes from a regional mortality register while for HM Hospitales, the vital status comes directly from hospital records. For IMRD UK and IPCI, the vitals status information comes from GP recording.

Section 8.0 Protection of Human Subjects

For this study, participants from various EU member states will process personal data from individuals which is collected in national/regional electronic health record databases. Due to the sensitive nature of this personal medical data, it is important to be fully aware of ethical and regulatory aspects and to strive to take all reasonable measures to ensure compliance with ethical and regulatory issues on privacy.

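### For objectives 2 and 3 the ITT analysis hangs on an inconsistently worded 70% censoring trigger, and the end of exposed time is not fixed consistently

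*Protocol*

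**What the plan says.** All places are in the protocol.

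**When the ITT analysis runs.** Section 7.3.2.3 (exposure groups for incidence calculation): "In case that more than 70% of the patients are censored, a sensitivity approach will be applied for objectives 2 and 3", with a reference to section 7.7.8. Section 7.7.8: "if the number of patients censored due to switching is higher than 70%, a sensitivity analysis will be performed". Section 7.9.1: "an ITT sensitivity analysis is proposed in case censoring is very large (>70"%), as mitigation for a limitation about glucocorticoids given as second or third treatment.

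**What ends exposed time.**
- Section 7.2.3: "The patients will be followed up for maximum 90 days or until censoring occurs, censoring criteria are" death, deregistration, end of the database's data collection and end of the study period. Neither switching nor stopping is listed.
- Section 7.3.2.3: exposure is on-treatment, first episode only, with censoring at a switch or at end of follow-up. "A persistence window of 7 days between drug utilization records for each study drug" counts as continuous exposure.
- Section 7.7.4: the rate uses person-time treated and repeats censoring at a switch. The incidence proportion divides events in patients on treatment by the population at risk at the start. Results are reported at 30 and 90 days.
- Section 7.7.8: the ITT denominator is person-time observed whatever the treatment status, set against person-time treated.

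**Course length and known weakness.** Section 7.3.2.3 (daily dose): "The current recommendation is to use 10 mg of dexamethasone for maximum 10 days". Table 3 gives rules for duration and end of treatment by database. Section 7.9.1 concedes that "this way of classifying exposure does not consider subsequent treatments and might miss a deterioration of disease".

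**The concern.** Two analysts could follow this protocol and differ on whether the ITT analysis is run at all, and on how long a treated patient is followed. A mortality or adverse-event result labelled 90-day might cover 90 days in one implementation and less than three weeks in another.

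The trigger also measures the wrong thing. Section 7.9.1 accepts that deterioration may be missed. Patients who change treatment because they are getting worse leave the on-treatment analysis before the event. That bias depends on who is censored, not on whether the censored share passes 70%.

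**Working it through.** The plan states no expected censoring share or on-treatment duration, so there is no figure of its own to reproduce.

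**1. The two triggers.** Section 7.3.2.3 lists end of follow-up as censoring. Read literally, its trigger fires when 1 − (share with the event) > 0.70, that is, for any outcome with incidence below 30%. Section 7.7.8 fires only when more than 70% switch. Assumed split: 20% switch, 60% stop, 10% have the event, 10% reach the end of follow-up. Censored for any cause: 20 + 60 + 10 = 90%. Censored by switching: 20%. One wording runs the ITT analysis and the other does not.

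**2. Length of follow-up for one short course.** Assumed course: 10 days, borrowed from the dexamethasone sentence.

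| Reading | Days | Share of 30 | Share of 90 |
|---|---|---|---|
| Ends at stop; 7 days only bridges gaps between records | 10 | 33% | 11% |
| Ends at stop plus 7 days | 10 + 7 = 17 | 57% | 19% |
| Only a switch or end of follow-up censors | up to 90 | 100% | 100% |

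Assumed courses of 5 to 30 days give 5 to 30 days without the tail and 12 to 37 with it.

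**3. Effect on the incidence proportion.** If exposed time ends at stop, the numerator is cut to on-treatment events while the denominator stays the full starting population. With constant hazard h = −ln(1 − r)/90 and 90-day risk r, the share captured by day t is (1 − exp(−ht))/r. For assumed r of 2%, 10% and 26%, 17 days captures 19%, 20% and 21% of the 90-day risk; 10 days captures 11%, 12% and 13%. Under a constant hazard the rate per patient-day would not be biased by this truncation; the proportion would.

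**4. Switching related to prognosis, ignoring stopping.** The 26% mortality is the UK inpatient figure in section 5.0 (given as over 26%). The rest is assumed: 1,000 inpatients, a 30-day horizon, deaths on day 10, switches on day 4.

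No censoring: 260/(740×30 + 260×10) = 260/24,800 = 10.5 per 1,000 patient-days.

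Switching in 80% of those who die and 30% of survivors: 52/(52×10 + 208×4 + 518×30 + 222×4) = 52/17,780 = 2.9.

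| Switching: died / survived | Overall | Deaths counted / patient-days | Rate per 1,000 | Fold low |
|---|---|---|---|---|
| 80% / 30% | 43% | 52 / 17,780 | 2.9 | 3.6 |
| 60% / 20% | 30% | 104 / 20,016 | 5.2 | 2.0 |
| 50% / 50% | 50% | 130 / 14,400 | 9.0 | 1.2 |

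Every row is below 70%, so the section 7.7.8 trigger is silent. In the first row 430 switchers plus 518 survivors at end of follow-up are censored, 94.8%, so the literal section 7.3.2.3 trigger fires on the same data.

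The last row is low although switching there is unrelated to outcome; that comes from fixing the days. As a benchmark, 43% switching in both groups gives 148.2/(148.2×10 + 111.8×4 + 421.8×30 + 318.2×4) = 148.2/15,856 = 9.3, or 1.1-fold low. Most of the 3.6 in the first row is therefore due to prognosis-related switching under these assumptions.

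**The case against.** **The trigger may be one rule, loosely worded.** Section 7.9.1 mitigates a sentence about later glucocorticoid treatment, so it concerns switching, and section 7.3.2.3 defers to section 7.7.8. This largely stands. A reader might infer that two sections count censoring for any cause; the documents support that only for the literal wording of section 7.3.2.3. The conflict between 7.3.2.3 and 7.7.8 remains on the page.

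**The plan does not say 17 days.** Correct. The 10 days is a dexamethasone recommendation, five drugs qualify, and the 7 days is worded as a gap between records. A reader might infer that 90-day results really cover 17 days; what the documents support is a range of about 10 to 90 days depending on the reading.

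**The end of treatment is discernible.** Table 3 and the inferred end dates supply it. They do, but no censoring rule uses them.

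**The untreated group.** A reader might infer that it always runs to day 90. Starting treatment would plausibly censor it too, and section 6.3 puts comparison with untreated patients out of scope. This stands.

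**Safeguards exist.** Reasons for censoring and follow-up duration per treatment cohort will be reported. These reveal the problem but do not correct a biased rate.

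**On-treatment was chosen for a reason.** Section 7.9.1 cites comparability with trial results. This stands: the documents do not support making ITT the source of every 30- and 90-day result. With a 17-day exposure, 73 of 90 days would be off drug, diluting acute steroid effects.

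**Conclusion.** The concern holds for the secondary objectives 2 and 3; the primary utilisation objective is untouched. Two defects are on the page: a trigger that names no cause in section 7.3.2.3 but names switching in section 7.7.8, and on-treatment person-time with no rule that ends it at stopping.

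The ambiguity in follow-up, roughly 10 to 17 days against up to 90, rests on the borrowed 10-day course. The 1.2- to 3.6-fold understatement rests on assumed switching shares, fixed days and a UK fatality figure, whereas the only hospital database is Spanish. It shows what can go unchecked below 70% and is not a forecast. A trigger based on the amount of censoring cannot detect censoring related to prognosis, whatever the true size.

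**What to change.** 1. Delete the 70% condition in sections 7.3.2.3, 7.7.8 and 7.9.1. Report the ITT analysis already specified in section 7.7.8 alongside the on-treatment analysis for every objective 2 and 3 outcome, at 30 and 90 days.
2. Reconcile sections 7.2.3, 7.3.2.3, 7.7.4 and 7.7.8 with one analysis rule for the end of exposed time, tied to the treatment end date derived under section 7.3.2.3 and Table 3. State whether the 7 days only bridges gaps between records or also extends exposure after the last one. Name switching and stopping in section 7.2.3 as they apply.
3. Label on-treatment results as on-treatment and show follow-up time per group beside each 30- and 90-day figure.

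The on-treatment analysis may remain the main one. The cost is wording in a few sections and one further run of an analysis already specified. The small downside is that ITT follow-up includes off-drug time, which is why both results should be shown.

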7.3.3 Adverse events

The following acute adverse events will be evaluated in the glucocorticoid treated patients and patients treated with alternative therapies:

- Composite cardiovascular events (composite of ischemic stroke, haemorrhagic stroke, heart failure, acute myocardial infarction or sudden cardiac death)
- Hypertension
- Arrhythmia
- Gastritis, gastric ulcer, GI bleed
- Psychosis
- Myopathy
- Hyperglycaemia
- Infections
- Any bacterial infection
- Any viral infection
- Any fungal infection
- Any parasitic infection

And if numbers allow, within infections, also separately look at:

- Sepsis
- Lower respiratory tract infections
- Herpes zoster
- Cutaneous cellulitis

7.3.4 Disease severity outcomes

In ambulatory care cohorts

- Hospital admission
- Venous thromboembolism (VTE) or pulmonary embolism (PE)
- Disseminated intravascular coagulation (DIC)
- Death of any cause

In hospitalized cohorts

- Intensive services as an outcome in inpatient cohorts (including mechanical ventilation and Extracorporeal membrane oxygenation (ECMO))
- Discharge from hospital
- Death of any cause
- Venous thromboembolism (VTE) or pulmonary embolism (PE)
- Disseminated intravascular coagulation (DIC)

They will all be treated as time to event outcomes, see section 7.7 for details.

7.3.5 Other Variables

Age – measured both as continuous and categorical variable in years. The following categories will be created:

- <18
- ≥18 and <65
- ≥ 65 and <75
- ≥75

Sex

- Male
- Female

Index month of diagnosis

Comorbidities

- Hypertension
- Type 2 diabetes mellitus
- Chronic obstructive pulmonary disease (COPD)
- Asthma
- Chronic kidney disease
- Ischemic stroke or haemorrhagic stroke
- Heart failure
- Acute myocardial infarction
- Arrhythmia

- Venous thromboembolism (VTE) or pulmonary embolism (PE)
- Obesity (using diagnosis codes)
- Smoker
- Alcohol/Drug abuse
- Autoimmune conditions (type 1 diabetes mellitus, rheumatoid arthritis, psoriasis, psoriatic arthritis, multiple sclerosis, systemic lupus erythematosus, Addisons, Graves, Sjogrens, Hashimoto, myasthenia gravis, autoimmune vasculitis, pernicious anaemia, celiac disease, scleroderma, sarcoid, ulcerative colitis, Crohn disease)
- Organ transplantation,
- Cancer
- Dementia,
- Major psychiatric disorder

These will be used to describe the cohorts at relevant index dates(s) and some of these will be selected as risk factors/confounders for the incidence rates analysis, see section 7.7 for details.

Respiratory support

Patients will be considered having adjunctive respiratory support if available medical records data are available for the following interventions on or post COVID-19 diagnosis:

- Any type of respiratory support
- Invasive mechanical ventilation (including ECMO)
- ECMO only

If no records are observed, then the patient will be considered as receiving no respiratory support.

7.4 Data Sources

Longitudinal Patient Database (LPD) Belgium (IQVIA)

LPD Belgium is a computerised network of general practitioners (GPs) who contribute to a centralised database of anonymised data of patients with ambulatory visits. Currently, around 300 GPs from 234 practices are contributing to the database covering 1.1M patients from a total of 11.5M Belgians (10.0%). The database covers a time period from 2005 through the present. Observation time is defined by the first and last consultation dates. Drug information is derived from GP prescriptions. Drugs obtained over the counter by the patient outside the prescription system are not reported. No explicit registration or approval is necessary for drug utilisation studies.

Longitudinal Patient Database (LPD) France (IQVIA)

LPD France is a computerised network of physicians including GPs who contribute to a centralised database of anonymised patient EMR. Currently, >1200 GPs from 400 practices are contributing to the database covering 7.8M patients in France. The database covers a time period from 1994 through the present. Observation time is defined by the first and last consultation dates. Drug information is derived from GP prescriptions. Drugs obtained over the counter by the patient outside the prescription system are not reported. No explicit registration or approval is necessary for drug utilisation studies.

Disease Analyser (DA) Germany (IQVIA)

DA Germany is collected from extracts of patient management software used by GPs and specialists practicing in ambulatory care settings. Data coverage includes more than 34M distinct person records out of a total population of 80M (42.5%) in the country and collected from 2,734 providers. Patient visiting more than one provider are not cross-identified for data protection reasons and therefore recorded as separate in the system. Dates of service include from 1992 through present. Observation time is defined by the first and last consultation dates. Germany has no mandatory GP system and patient have free choice of specialist. As a result, data are collected from visits to 28.8% General, 13.4% Orthopaedic Surgery, 11.8% Otolaryngology, 11.2% Dermatology, 7.7% Obstetrics/Gynaecology, 6.2% various Neurology and Psychiatry 7.0% Paediatric, 4.6% Urology, 3.7% Cardiology, 3.5% Gastroenterology, 1.5% Pulmonary and 0.7% Rheumatology practices. Drugs are recorded as prescriptions of marketed products. No registration or approval is required for drug utilisation studies.

IQVIA Medical Research Data (IMRD) UK (IQVIA)

IMRD UK is a large database of anonymised electronic medical records collected at Primary Care clinics throughout the UK. Data coverage includes 15.2M patients, 5.6M providers, 793 care sites and more than 5 billion service records, covering 22.5% of a population of 67.5M. Dates of service include from 1996 through present. Quality indicators define the start date for that patient (e.g. each patient's observation period began at the latest of the patient's registration date, the acceptable mortality recording date of the practice, the Vision date). The end of the observation period is determined by the end date of registration in the database. Drug treatment is recorded as prescriptions. All protocols must be submitted to an independent Scientific Review Committee prior to study conduct.

Longitudinal Patient Database (LPD) Italy (IQVIA)

LPD Italy is comprised of anonymised patient records collected from software used by GPs during an office visit to document patients' clinical records. Data coverage includes over 2M patient records with at least one visit and 119.5M prescription orders across 900 GP practices. Dates of service include from 2004 through present. Observation time is defined by the first and last consultation dates. Drugs are captured as prescription records with product, quantity, dosing directions, strength, indication and date of consultation.

Integrated Primary Care Information (IPCI), The Netherlands

IPCI is collected from EHR records of patients registered with their GPs throughout the Netherlands. The selection of 391 GPs is representative of the entire country. The database contains records from 2.6 million patients out of a Dutch population of 17M (8.2%) starting in 1996. The median follow-up is 2.2 years. The observation period for a patient is determined by the date of registration at the GP and the date of leave/death. The observation period start date is refined by many quality indicators, e.g. exclusion of peaks of conditions when registering at the GP. All data before the observation period is kept as history data. Drugs are captured as prescription records with product, quantity, dosing directions, strength and indication. Drugs not prescribed in the GP setting might be underreported. Indications are available as diagnoses by the GPs and, indirectly, from secondary care providers but the latter might not be complete. Approval needs to be obtained for each study from the Governance Board. (5) The IPCI database is currently increasing the update frequency because of the COVID-19 pandemic (now updated till March 2020).

Information System for Research in Primary Care (SIDIAP), IDIAP Jordi Gol (Spain)

SIDIAP is collected from EHR records of patients receiving primary care delivered through Primary Care Teams (PCT), consisting of GPs, nurses and non-clinical staff. The Catalan Health Institute manages 286 out of 370 such PCT with a coverage of 5.6M patients, out of 7.8M people in the Catalan population (74%). The database started to collect data in 2006. The mean follow-up is 10 years. The observation period for a patient can be the start of the database (2006), or when a person is assigned to a Catalan Health Institute primary care centre. Date of exit can be when a person is transferred-out to a primary care centre that does not pertain to the Catalan Health Institute, or date of death, or date of end of follow-up in the database. Drug information is available from prescriptions and from dispensing records in pharmacies. Drugs not prescribed in the GP setting might be underreported; and disease diagnoses made at specialist care settings are not included. Studies using SIDIAP data require previous approval by both a Scientific and an Ethics Committee (9).

Hospital de Madrid (HM) Hospitales (Spain)

Hospital de Madrid (HM) Hospitales data are made available through partnership with SIDIAP. The HM Hospitales database covers in-patient care delivered across a network of private hospitals in Spain. HM Hospitales covers more than 17M patients, out of whom a subset will be catalogued and followed for acute care delivered for suspected COVID-19 onset. This database covers more than 2300 confirmed COVID-19 cases and all in-patient hospital care, including the data of admission, conditions, procedures and medicines dispensed in hospital, date of discharge, and date of known death or date of end of follow-up in the database. Studies using HM Hospitales data require review and approval from data custodians at SIDIAP authorised to execute observational network analyses. The number of newly diagnosed patients in each database per month since the outbreak of COVID-19 can be derived from the databases.

None of the databases, except SIDIAP have linkage between primary and secondary care setting.

A database profiling, describing a range of variables in terms of data quality and completeness, as well as attrition tables for COVID-19 populations can be found at the following link:

https://dqdashboard.iqvia.com/ema_report1/.

